#### Reporting Procedures

- Data and safety monitoring reports will be sent to the IRB every 6 months during the adverse event reporting period.

#### Adverse Event Reporting Period

- Initiation of enrollment (May 1, 2023) through March 30, 2024.

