**C4e. Sample Size, Power, and Attrition.** This trial aims to recruit a sample of 72 (36 in each group), which is a pragmatic decision based on the patient pool, budget, and two-year study period. We will recruit patients from the Health Hub and Tennessee Population Health Data Network (TN- POPnet). Given the study has broad eligibility criteria, we anticipate an estimated 20 adult patients with diabetes and obesity being eligible each month. This will provide a sufficient pool to enroll 8 patients/month and 72 patients over 9 months. We expect that after accounting for 15% attrition at 12-month follow-up, about 61 study participants will complete the study. The attrition rate is based on the evidence from our MODEL study and from Lean *et al.* This pilot study will help us to estimate the following: 1) Effect size for the study intervention, 2) Total number patients recruited, 3) Number of patients recruited each month, 4) Total time required to recruit patients, 5) Number of patients retained, and 6) Barriers and facilitators to recruitment and implementation of the interventions. The research will employ intensive *scientific rigor* in every stage of design and conduct to ensure robust and unbiased experimental design, methodology, analysis, interpretation, and reporting of results and the ability to reproduce the research findings.

**C5. Multicomponent Motivational Interventions.** All component interventions received by both the treatment and control groups will be delivered in phases as shown in **Table 2** below.

**C5a. Intensive Preparation for Change and Core Educational Interventions.** All patients will receive introductory education on plant-forward healthy eating for weight loss. Health coaches will lead two sessions (introductory and kickoff) for the treatment group; pharmacists or nutritionists will lead one traditional diabetes education session for the control group. All patients will receive evidence-based self-care tools included in the MODEL program toolkit adapted from DPP, ACT, Look AHEAD, and TARGIT, and supplemental recipe and diet information adapted from DiRECT and the Daniel Diet program. Treatment group participants will also receive training in cognitive behavioral strategies employing these tools.

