### **C8. Study Visits.**

Screening Visit. Eligibility will be assessed. A1c will be obtained from through a blood draw (less than 1 teaspoon of blood) through a finger stick. [name] will assay the patient's sample for HbA1c using the analyzer in the UT Endocrinology Lab to assess potential eligibility. In addition, patient's weight, height, BMI, and blood pressure will be measured using the scales the appropriate scales and validated protocols. Participants will also be required to provide a list of their current medications and name and contact information of the primary care provider in event that they are randomized into the intervention arm at the baseline visit. Participants will be informed of their rights to determine who has access to their personal health information (PHI) in compliance with HIPPA regulations. As part of informed consent patients will be extensively counseled regarding all components of the treatment and control interventions to confirm their interest and willingness to participate in all component interventions prior to enrollment. After informed consent, contact and demographic information will be obtained. If a study participant has difficulty reading the informed consent or other study data collection forms, project personnel will assist. At this visit, all baseline study measures will be obtained.

Baseline Visit. Following confirmation of eligibility at the screening visit, potential participants will be scheduled for a baseline visit at the health hub. Eligible participants will be randomly assigned to one of the two arms and informed of their group assignment. Participants will be randomized to the HEAL Diabetes arm or the usual care condition. We will randomize 20-24 participants for each recruitment wave, for a goal of approximately 12 per condition. Participants will be randomized 1:1 to the two study conditions in randomly permuted blocks of size 8 using SAS random allocation. The randomization list was generated through SAS at the start of the study before randomization. The list is managed by one of the PIs. Once a participant has been determined to be eligible, the PI will assign each participant to the next open assignment on the list. We will tell

them at the Baseline visit which group they were assigned. Additionally, participants will have their first introduction to the health coaches.

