Follow-up visits 1–3. Outcomes will be assessed at the end of three months (Follow-up 1), 6 months (Follow-up 2) and at one-year (Follow-up 3). All survey measures described below will be conducted at the health hubs.

Additional In-Person Visits for intervention group:

- Individual health coaching over 6 months (14 sessions total) (1 hour)
- Group support sessions (6 sessions total) (1.5 hours)
- Cooking/Nutrition classes (6 sessions total) (2 hours)

**C9. Participant Retention.** Our procedures will include the following strategies to track and retain participants: 1) collecting names, addresses, and phone numbers of relatives and friends who will usually know the participant's whereabouts; 2) contacting participants with personalized letters and cards and remembering them at special times such as birthdays and holidays; 3) maintaining phone contact with participants throughout the study; 4) setting up a tracking database with names, addresses, phone numbers, email addresses, social media page information, and projected time windows; 5) taking a case management approach for handling difficult retention cases.

Participant withdrawal. If participants withdraw from the protocol or fail to return for follow-up visits, we will continue to collect utilization and clinical data unless they withdraw consent. Data analysis will use best available follow-up weights and A1c values (closest within a window of  $\pm 3$  months from routine attendances) and end of study diabetes status for participants who discontinue the protocol. Drug intolerance, diet intolerance or poor compliance will be recorded; these patients will be included in intention-to-treat analyses.

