**F. Data and Safety Monitoring Plan.** Monitoring of the study is important for both assessment of safety of the intervention and interpretation of study results. We have a system for monitoring, scheduling, and tracking participants. Staff roles will clearly be delineated and there will be ongoing monitoring of the health education, nutrition support, and the health coaching provided. Participants will be followed for approximately one year. For any serious adverse event reported during the study, the nature, date of onset, duration, and resolution will be recorded. A co-investigator will monitor each participant for serious adverse events. If the serious adverse event is thought to be related to study participation by either the primary care provider and/or the physician investigators ([name]), the investigator may request the participant to undergo a physical examination, psychiatric evaluation, and/or laboratory testing whenever appropriate local to the participant. All staff members are trained on the FDA and IRB criteria and policies for a Serious Adverse Event. Study staff will be trained in assessing and reporting serious adverse events for all study populations.

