- [name], who is a co-investigator on this project, will have responsibility for analyzing interim data and preparing data and safety monitoring reports that the committee will review. These reports will include data on all adverse events and study outcomes for all study participants. [name] will be an ex-officio member of the committee and will not be blinded to participant group assignment. After the start of participant enrollment, we plan to conduct data and safety monitoring meetings in-person or via conference call twice a year. Data and safety monitoring reports will be sent to all committee members prior to the conference call.
- A Manual of Procedures will be developed for the study and the procedures will be strictly followed. All controlled trials personnel are trained in sessions that will cover all study procedures, including recruitment, informed consent, measurements, randomization, participant follow-up, and adverse events. Adherence to the procedures in the operations manual will be assured by periodic assessment and retraining. A co-investigator will monitor each participant for adverse events throughout the study using participant report and reports by primary care physician. All participants will be asked at each study visit about emergency visits, hospital visits, or other serious adverse events in the intervening period, and these reported events will be recorded in the study database. If significant differences in adverse events noted above are found, additional interviews of the participant experiencing these adverse events may be conducted at the discretion of the DSMB and any necessary remedial action taken will be recorded. At any point a participant may be withdrawn from the study for health-related reasons. Medical side effects of improvements in healthy eating, physical activity, and medication adherence will be explained as part of the informed consent process to each participant by trained study personnel and participants will be provided a copy of the informed consent statement that will include a written list of potential side effects prior to randomization. An attempt will be made to quantify the severity of each side effect by asking the participant to grade its importance or impact on quality of life.

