**F3b. Classification of Events.** In this study, the likelihood of serious adverse events associated with the planned interventions is very low, and mostly consists of a small possibility of serious hypoglycemic or hyperglycemic reactions associated with improvements in health habits as detailed below. All adverse events will be classified as to whether they are serious or not serious. An adverse event is considered serious if it is life threatening, prolonged or permanently disabling, requires or prolongs hospitalization for any cause other than routine delivery, is a congenital anomaly, or a major cardiovascular event. An event may also be considered serious if an investigator judges it to be a significant hazard or contraindication to continued study intervention or use of study medication. In addition, we will classify all adverse events regarding the relationship, severity, and expectedness as described below.

**Relationship** The following are expected adverse events that may occur during the trial:

**Related to Intervention.** Potential adverse events (AE) known to be associated with caloric restriction, weight loss, or improved medication adherence in patients with diabetes: hypoglycemia, hyperglycemia, malnutrition, bone loss, gall bladder disease. The DiRECT trial which employed a similar intervention found that severe hypoglycemia occurred between 0.2 to 0.57 times per 100 patient years in the treatment arm over the first 4 years of the study. Potential AE's known to be associated with exercise in patients with diabetes: hypoglycemia, fracture or other injury, cardiac arrhythmia, cardiovascular event.

**Related to condition under study.** Potential AE's known to be associated with overweight or obesity include: diabetes, hypertension, dyslipidemia, cardiovascular disease (CVD), gall bladder disease, liver disease. All patients will be monitored at every data collection visit through the 12-month visit for the occurrence of these adverse events.

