**Severity** During the trial participants will be queried to determine if a serious adverse event has occurred as described above and all adverse events will be identified through patient and provider report. All serious adverse events will be recorded. A serious adverse event is considered serious if it is life threatening, prolonged or permanently disabling, requires or prolongs hospitalization for any cause other than routine delivery, is a congenital anomaly, a major cardiovascular event, or cancer other than non-melanoma skin cancer. An event may also be considered serious if an investigator judges it to be a significant hazard or contraindication to continued study intervention or use of study medication.

**Expectedness** Adverse events will also be classified as to whether they are expected or unexpected. An unexpected adverse event is one for which the nature or severity is not consistent with information about the condition under study or intervention in the protocol, consent form, or program brochure. An expected event is one known to be associated with the intervention or condition under study. Thus, expectedness is related both to the intervention and to the condition under study. All serious or unexpected adverse events related to the intervention will be reported to the IRB and to the sponsor in a timely manner.

**F3c. Data Collection Procedures for Adverse Events.** As described above, a co-investigator will monitor each participant for serious adverse events throughout the study using participant and provider reports. All patients will be asked at each study visit about emergency visits, hospital visits, or other serious adverse events in the intervening period, and these reported events will be recorded in the study database and concordance with the registry assessed as described above. Participants will be asked at each study visit about any serious adverse events that may have occurred between study visits. All participants will be encouraged to contact the study site if untoward symptoms, illnesses, or hospitalizations of any nature occur. In addition, their relatives and their personal physicians will be asked to notify the study site of any hospitalizations or major illnesses. Conversely, if the health hub personnel uncover a morbid event in a study participant, the study staff will contact the participant's personal health care provider.

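### The adverse-event reporting period ends on March 30, 2024, before any participant can reach the nominal 12-month visit, and the six-monthly IRB safety reports end with it

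*Combined protocol and SAP*

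**What the plan says.** The short sections after F3c give the reporting rules. Under Adverse Event Reporting Period the whole entry is "Initiation of enrollment (May 1, 2023) through March 30, 2024". Under Reporting Procedures, safety reports go to the IRB at six-month intervals for as long as that period lasts. The Post-study Adverse Event entry says that none are expected and sets no later reporting window.

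The timetable elsewhere is longer:

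- Section C4e, on accrual: "This will provide a sufficient pool to enroll 8 patients/month and 72 patients over 9 months", within a two-year study period.
- Section C8 has enrolment in waves: "We will randomize 20-24 participants for each recruitment wave, for a goal of approximately 12 per condition". It places the last outcome visit at one year.
- Section F: "Participants will be followed for approximately one year".
- Section F3b: "All patients will be monitored at every data collection visit through the 12-month visit for the occurrence of these adverse events".

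Two other safety provisions carry no end date. Section F3b says "All serious or unexpected adverse events related to the intervention will be reported to the IRB and to the sponsor in a timely manner", and section F2d says that after enrolment starts "we plan to conduct data and safety monitoring meetings in-person or via conference call twice a year".

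**The concern.** The reporting period is a pair of calendar dates, while follow-up runs from each participant's own enrolment. A window shorter than one participant's follow-up cannot contain anyone's full year, however fast accrual goes. Because the IRB reports are tied to the window, following the text exactly ends them while every participant is still in follow-up. Staff would also have two end points to work from: March 30, 2024 for reporting, and the 12-month visit for monitoring.

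The follow-up left out is mostly the later months. Section C5d foresees that diabetes may return during weight-loss maintenance (months 5 to 12), and section C5g names hyperglycemia and hypertension as possible consequences of stopping medication. Late enrollees would still be in the diet-replacement phase when the window closes.

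**Working it through.** **Inputs.** Window: May 1, 2023 to March 30, 2024 (Adverse Event Reporting Period). Accrual: 8 per month, 72 in total, 15% attrition at 12 months (C4e). Follow-up: 12 months (C8, F). IRB reports: every six months within the window (Reporting Procedures).

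**The plan's own figures reproduce.** 72 / 8 = 9 months of accrual. 72 × 0.85 = 61.2, matching the stated 61 or so completers.

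**Length of the window.** 334 days / 30.4375 = 10.97 months. Needed: 9 + 12 = 21 months.

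**Earliest possible 12-month date.** May 1, 2023 + 12 months = May 1, 2024, 32 days after the close. This needs no accrual assumption. If baseline counts as month 1, as in Table 2, month 12 begins on April 1, 2024, still 2 days late.

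**Last participant.** With 9 months of accrual the last enrolment is about January 31, 2024, leaving 59 days (1.9 months) inside the window. The last 12-month visit is about January 31, 2025, 307 days (10.1 months) after the close.

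**Share of follow-up outside the window.** With enrolment at month t_i, the share is 1 − mean[min(12, 10.97 − t_i)] / 12.

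| Scenario | Mean months covered | Share outside |
|---|---|---|
| All enrolled on day one | 10.97 | 8.6% |
| Even accrual, t_i = (i − 0.5)/8, i = 1 to 72 | 10.97 − 4.5 = 6.47 | 46.1% |
| Three waves of 24 at months 0, 3, 6 | 10.97 − 3 = 7.97 | 33.6% |
| Three waves of 24 at months 3, 6, 9 | 10.97 − 6 = 4.97 | 58.6% |

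These assume no dropout. Spreading 15% attrition linearly over the year changes the even-accrual figure to 44.4%. Monthly cohorts of 8 enrolled at the start or end of each month, rather than mid-month, give 42% or 50%. The protocol gives no wave dates, so the wave rows are assumptions.

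**Milestones reached by March 30, 2024, at even accrual.** Month 3: 64 of 72. Month 4 (scheduled end of diet replacement): 56 of 72. Month 6: 40 of 72, or 24 to 48 with the waves above. Month 12: 0 of 72.

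**IRB reports.** Counting six months from May 1, 2023 (an assumption; no first report date is given), the due dates are November 1, 2023, May 1, 2024 and November 1, 2024. Only the first is inside the window. With a first report by September 30, 2023, a second could fall due by March 30, 2024. The text therefore supports one report, or at most two.

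**Six-month horizon.** The Abstract speaks of outcomes over six months and at least 30 + 30 = 60 patients. At 8 per month that needs 60/8 + 6 = 13.5 months, and with 72 patients 9 + 6 = 15. Both exceed 10.97.

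**The case against.** The strongest reply is that little safety oversight is lost. Participants are asked about events at every visit. Serious or unexpected related events go to the IRB and the sponsor whenever they occur. The study team reviews progress monthly (F1b), and an independent board meets with no end date. No endpoint, analysis or participant-level safety record changes. Most participants would finish diet replacement, with its weekly glucose and blood-pressure checks, inside the window (56 of 72 at even accrual). On this view the date is an administrative slip.

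Much of that stands: this is a reporting error, and the percentages describe time outside a defined period, not lost surveillance. But the continuing provisions do not replace the periodic IRB report. Event-level reporting covers only events judged related to the intervention, and the board's reports go to the board.

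Three narrower objections deserve weight:

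- The F3b sentence on monitoring through 12 months concerns collection, not reporting, and sits in the paragraph on events related to the underlying condition. The clash with it is therefore less direct than the clash with the one-year follow-up in C8 and F, which is enough by itself.
- The report count depends on when the six-month clock starts.
- Follow-up is only approximately one year and no visit window is defined for continuing participants, so the zero of 72 refers to nominal dates. The ±3-month allowance in C9 concerns values for participants who discontinue and does not move the scheduled visit.

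**Conclusion.** The stated end date is wrong for the trial described. That conclusion rests only on printed dates and the 12-month follow-up: even a day-one enrollee misses the window by 32 days, and at least 8.6% of planned follow-up lies outside it. The larger figures depend on accrual: about 46% outside at the planned even rate, and 34% to 59% under the assumed wave dates. Read literally, the IRB receives one periodic safety report, or two on a different cycle, instead of a series running to about the end of January 2025. The consequence is a gap in periodic IRB reporting and an internal contradiction over when adverse-event reporting ends. It is not a lapse in participant-level safety monitoring. The error is certain and cheap to correct, so it should be corrected.

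**What to change.** In Adverse Event Reporting Period, replace the fixed end date with a participant-based rule: from first enrolment to the 12-month visit of the last enrolled participant. At planned accrual that is about the end of January 2025, and the rule adjusts itself if recruitment is slower. In Reporting Procedures, continue the six-monthly IRB reports to that point with a closing report, and state the date from which the six months are counted. Check the result against C4e, C8, F and F3b so that all give the same end point.

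The cost is a short amendment and, on a May 1, 2023 clock, two more periodic reports (May and November 2024) plus the closing one. No visit, question or meeting is added, because these are already planned.

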#### Post-study Adverse Event

- Not expected

## **G. Ethical Considerations.**

**G1. Informed Consent.** The consent process will take place at the beginning of the baseline appointment. We will allow time for discussion or questions about the study. Consent will be obtained by study personnel trained in the consent process. To be able to participate in the study, participants must be adults without impaired decision-making ability that are able to speak, read, and understand English. The consent process will include a discussion of the participant's understanding of what their participation in the study means, which will include, discussion of their rights, the protocol, all potential risks and benefits, and their options and contacts to express any concerns or complaints. A copy of the consent form has been provided with this application.

**G2. Risks and Side Effects.** Possible risks for being in this study include hypoglycemia, gallstones, temporary discomfort, or mental anguish adapting to the behavioral changes (i.e., new diet, increased movement and activity), and possibly breach of confidentiality and privacy by other participants during nutrition education classes. We will have procedures in place to minimize the potential for risks and side effects for participants.

- A possible side effect, Hypoglycemia, is a condition in which an individual's blood sugar (glucose) level is lower than the standard range. Participants will be carefully monitored and counseled on ways to decrease the risk of hypoglycemia. Staff and patients will be trained to recognize the signs and symptoms of hypoglycemia, in addition, a physician is available to provide supervised medication discontinuation for every participant.
- Gallstones are expected to be very rare (Less than 1% risk). However, this discomfort usually resolves or greatly diminishes within one week as long as participants stick with their healthy diet. This potential risk is not serious and is completely reversible. Participants will be carefully monitored and counseled on ways to decrease the risk of gallstones.
- Regarding discomfort and mental anguish, participants will be advised of the risks and benefits of participation and informed of their right to withdraw from the study at any time if they should choose to discontinue. Finally, participants will be advised on informed consent and their role in protecting the confidentiality and privacy of other participants and their own.
- Randomization: Although it is expected that both study treatments will be either beneficial or neutral (with no effect at all), it is possible that the treatment that a participant is assigned to, may later be shown to be less effective than other therapies.

**G3. Benefits.** Participants may or may not benefit from participating in the study. Benefits that may occur include weight loss and/or diabetes remission. Another tangible benefit for the experimental group is receipt of food subsidies during the study timeframe, while the control group will receive food vouchers. Societal benefits include providing evidence to support the use of multi-component behavioral change interventions to treat obesity and diabetes. Additionally, this research will contribute to a growing body of research on treating diabetes and other chronic illnesses using the 'food as medicine' hypothesis or medically-tailored meals as an alternative to traditional treatment.

**G4. Alternatives to Participation.** Should individuals choose not to participate, they have the option of standard care through options already available to them. Another alternative to participation is the health hub, where health coaches provide support in weight loss, blood pressure control, healthy eating strategies, physical activity, and medication adherence.

**G5. Costs to Subjects.** Costs to subjects include time investment and transportation expenses, but participants can be helped with free medical transportation. Economic burden to subjects includes the time needed for screening and study participation. Regarding the time commitment, we will do our best to work with subjects' schedules, so that any possibly resource-vulnerable individuals are not required to miss work or other important obligations in exchange for their participation. While there is no cost to participation in the study, if participants elect to receive motivational text messages, standard texting rates will apply.

**G6. Compensation to Subjects.** Although there are many potential benefits to participation, subjects will not receive monetary compensation outside of the food subsidies, food vouchers, and transportation expenses (as needed).

**G7. Provisions for Vulnerable Subjects.** The patient sample for this study is likely to include economically disadvantaged persons, as well as racial/ethnic minorities. Additionally, this study may unintentionally or unknowingly include participants who are considered decisionally-impaired due to psychiatric, cognitive or developmental disorders, substance abuse problems or individuals in chronic pain. The study team will take all necessary steps to assure that participants in this study are fully informed about and understand the study, as

well as their rights and protections. We will thoroughly explain the risks, benefits, costs, privacy, confidentiality, and ability to withdraw or refuse participation. Participants will undergo the consent process at baseline and will know that their participation in this study is voluntary and they have a right to refuse or withdraw participation at any point in the study. Individuals who are decisionally-impaired may still be capable of providing consent. If evidence is present that they are incapable of providing informed consent due to the incapacity to understand, an individual who is legally authorized to consent for them must sign and date the consent document in order for them to be included in the study.

**G8. Subject Privacy and Data Confidentiality.** REDCap will be used for data entry and management. Digital recorders will be used for recording audio from the group nutrition classes/support group sessions. The database and recordings will be maintained on UTHSC servers where security will be maintained through access controls. Once recordings are saved on the server they are deleted from the recorder. Recordings are used only for quality control and will not be transcribed. Access to the files will require permission from the program director, a UTHSC password, and IRB personnel approval. For each user, REDCap will require a REDCap profile, username and password to enter the program. Study personnel will only have access to the database if the data manager has given them access. UTHSC IRBs and their representatives, and study personnel will have access to the research data, as will the study sponsor if requested. All participants will be assigned an ID number, which will link them to their study data. PHI fields will be stored in a separate form from other data collection forms. Data will be completely de-identified once the last assessment phase is complete. At this time the link between ID number and study data will be destroyed. Study data in the form of hard copies will be stored in a locked file cabinet managed by the program director and will be destroyed 3 years after completion of the study.

**H. Conflicts of Interest.** There are no conflicts of interest for the PI or any member of the study team.

**I. Plans for Dissemination of Findings.** We will disseminate study findings through regional and national scientific meetings in the form of presentations and reports.

